6.5.1. Rescue Medication

Participants may transiently use (ie, for <4 weeks) increased doses of corticosteroids for reasons other than loss of response to treatment for Crohn's disease (eg, stress doses of corticosteroids for surgery, asthma, adrenocortical insufficiency, etc).

Although enrolled participants should not initiate or increase the dose of oral or rectal 5-ASA compounds, immunomodulators (ie, AZA, 6-MP, or MTX), corticosteroids, or antibiotics as a treatment for Crohn's disease so as not to confound the efficacy assessments, it is recognized that the use of such compounds may be medically necessary. In such cases, participants may continue to receive the study intervention, but would be considered a treatment failure. This would not represent a deviation from the study protocol.

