6.5.2. Crohn's Disease-Specific Therapies

Participants must continue to receive their concomitant, background oral 5-ASA compounds, the immunomodulators AZA, 6-MP, and MTX, oral corticosteroids, and/or antibiotics for the treatment of Crohn's disease during the study (as defined in the inclusion criteria). **Concomitant medications for Crohn's disease at study enrollment should be maintained at a stable dose throughout this study.**

Enrolled participants **should not initiate** any of the following Crohn's disease-specific medical therapies during their participation in the study:

- Oral or rectal 5-ASA compounds
- Immunomodulators (ie, AZA, 6-MP, or MTX)
- Parenteral or rectal corticosteroids
- Antibiotics as a treatment for Crohn's disease
- Total parenteral nutrition as a treatment for Crohn's disease

Because protection of human research participants is paramount, it is recognized that initiating or modifying the dose of the above therapies may be medically required. If the above medications are initiated or medication doses are changed, participants may continue to receive the study

intervention, and should continue to attend all study visits and have all assessments. If due to medical necessity in the opinion of the investigator, the above medications are initiated or medication doses are changed, this does not represent a deviation from the study protocol, but may be considered a treatment failure.

Oral corticosteroid should not be initiated during the study.

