### **Treatment Failure Rules:**

Treatment failure rules will be applied for all efficacy endpoints unless otherwise specified. In such a case, baseline values (at Week 0) will be assigned from the point of treatment failure onward, regardless of the observed data, for continuous endpoints, and participants will be considered as not achieving the respective endpoints for dichotomous endpoints. Treatment failure rules override other data handling rules.

For dichotomous endpoints, participants who have a treatment failure are considered as not achieving the respective endpoints after treatment failure. For continuous endpoints, participants who have a treatment failure will have their baseline values carried forward after treatment failure onwards.

The treatment failure rules will be applied to determine the final CDAI score. The treatment failure rules override the actual observation of the CDAI score. Participants who have any of the following events prior to the Week 12 visit will be considered a treatment failure and will be considered to have no change at Week 12 from their baseline CDAI score, regardless of the actual CDAI score:

- A Crohn's disease-related surgery (with the exception of drainage of an abscess or seton placement)
- Discontinuation of study intervention due to lack of efficacy or due to an adverse event (AE) of worsening Crohn's disease
- Specified changes in concomitant Crohn's disease medications described below.

The treatment failure rules for physician prescribed concomitant medication changes between Week 0 and Week 12 are:

1. Corticosteroids:
  - a. Initiation of oral corticosteroids (excluding budesonide) due to worsening Crohn's disease.
  - b. Initiation of oral corticosteroids (excluding budesonide) for more than 7 days due to reasons other than worsening Crohn's disease.
  - c. Initiation of oral budesonide due to worsening Crohn's disease.
  - d. Initiation of oral budesonide for more than 7 days due to reasons other than worsening Crohn's disease.
  - e. Increase by  $\geq 5$  mg above baseline in the prednisone equivalent dosage of oral corticosteroids (excluding budesonide) due to worsening Crohn's disease.
  - f. Increase by  $\geq 5$  mg above baseline in the oral prednisone equivalent dosage of oral corticosteroids (excluding budesonide) for more than 7 days due to reasons other than worsening Crohn's disease.

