  - g. Increase by  $\geq 3$  mg above baseline in the dose of oral budesonide due to worsening Crohn's disease.
  - h. Initiation of IV corticosteroids due to worsening Crohn's disease.
  - i. Initiation of rectal corticosteroids due to worsening Crohn's disease.
2. 5-ASA compounds:
  - a. Initiation or increase of oral 5-ASA compounds due to worsening Crohn's disease.
3. Immunomodulator agents:
  - a. Initiation of oral 6-MP/AZA due to worsening Crohn's disease.
  - b. Initiation of oral, subcutaneous, or intramuscular MTX due to worsening Crohn's disease.
  - c. Increase above baseline in the dose of oral 6-MP/AZA due to worsening Crohn's disease.
  - d. Increase above baseline in the dose of oral, subcutaneous, or intramuscular MTX due to worsening Crohn's disease (with the same route).
4. Protocol-prohibited medications:

An initiation of any of the following after baseline due to worsening Crohn's disease:

  - a. Immunomodulatory agents other than 6-MP/AZA or MTX (including but not limited to 6-TG, cyclosporine, tacrolimus, sirolimus, mycophenolate mofetil).
  - b. Immunomodulatory biologic agents (including but not limited to TNF antagonists, natalizumab, abatacept).
  - c. Experimental Crohn's disease medications (including but not limited to thalidomide, briakinumab, vedolizumab, traficet, AMG 827).
5. Crohn's disease related antibiotics:
  - a. Initiation or change of antibiotics due to worsening Crohn's disease.

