### Intercurrent Events and Corresponding Strategies:

The following are the intercurrent events considered for this trial:

1. A Crohn's disease-related surgery (with the exception of minor procedures such as drainage of a superficial abscess or seton placement, etc.);
2. A prohibited change in CD medication;
3. Discontinuation of study intervention due to lack of efficacy or an AE of worsening Crohn's disease;
4. Discontinuation of study intervention due to COVID-19 related reasons (like missing the assessment visit due to COVID-19 quarantine, but excluding COVID-19 infection)
5. Discontinuation of study intervention due to reasons other than lack of efficacy or an AE of worsening Crohn's disease (including AE/SAE due to COVID-19 infection).

Intercurrent events (ICEs) in categories 1-3 will be handled by the composite strategy, and ICE category 4 will be handled by the hypothetical strategy (as if subjects would have not experienced this intercurrent event), and ICE category 5 will be handled by the treatment policy strategy. The composite strategy assesses the treatment effects not only based on the variable measurements, but also based on intercurrent events. This estimand acknowledges that having an intercurrent event in categories 1-3 is an unfavorable outcome, ie. baseline value will be used after ICEs. For subjects experiencing ICE category 4, CDAI data at all visits after an ICE will be set to missing with

assumption of missing at random. For ICE category 5, treatment policy strategy, the observed values after ICEs will be used, if available.

**Population-level summary:** The difference of change in the CDAI score at Week 12 between the Experimental treatment group and the placebo treatment group.

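### The SAP's medication failure rules do not match protocol 6.5.1: rectal 5-ASA has no rule, and the trigger 'worsening' is undefined

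*SAP*

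**What the plan says.** **Protocol 6.5.1 (Rescue Medication)** says participants should not "initiate or increase the dose of oral or rectal 5-ASA compounds, immunomodulators", corticosteroids or antibiotics to treat Crohn's disease, but accepts that this may be medically necessary. It then says: "In such cases, participants may continue to receive the study intervention, but would be considered a treatment failure". It attaches no condition about worsening.

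**Protocol 6.5.2**, on largely the same drugs (its list also names rectal 5-ASA), is softer: "this does not represent a deviation from the study protocol, but may be considered a treatment failure".

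**SAP 5.3.1 (Treatment Failure Rules)** assigns the baseline CDAI from the point of failure onward, whatever was observed. Its medication list works as follows.
- Rule 2a: "Initiation or increase of oral 5-ASA compounds due to worsening" Crohn's disease. Only the oral route is named.
- Rule 1g, for a budesonide increase: "mg above baseline in the dose of oral budesonide due to worsening" Crohn's disease. Rules 1h and 1i (IV and rectal corticosteroids), 3a-d (6-MP/AZA and MTX) and 5a (antibiotics) carry the same condition.
- Rules 1b, 1d and 1f (oral corticosteroids and budesonide) add failure for use "for more than 7 days due to reasons other than worsening" Crohn's disease. The other drug classes have no such companion rule.
- Stopping study drug is a failure under separate wording: "Discontinuation of study intervention due to lack of efficacy or due to an adverse event (AE) of worsening" Crohn's disease.

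**SAP 5.3.2.1** lists intercurrent event 2 as "A prohibited change in CD medication", with no definition there. **SAP 5.3.3.1** enters all collected CDAI values into the MMRM unless an intercurrent event changes them.

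**The concern.** The same participant can receive two different primary-endpoint values depending on which document, or which reading of one word, is followed.

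The clear case is rectal 5-ASA. The protocol names it as rescue that counts as failure, and the SAP list does not contain it.

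The less clear case is rescue because study drug is not working, in a participant who has not deteriorated. If 'worsening' is taken literally, such a participant who stays on study drug keeps the on-rescue CDAI. One who stops study drug for lack of efficacy is scored as no change.

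The affected value enters the primary MMRM, the Week 12 CDAI decision criterion (80% lower confidence bound of at least 40) and the CDAI responder endpoints. SAP 5.3.1 applies the same endpoint definition at the interim analysis.

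**Working it through.** **1. Compare the triggers.**

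| Rescue given for Crohn's disease, study drug continued | Protocol 6.5.1 | SAP list, 'worsening' read as any Crohn's reason | SAP list, 'worsening' read literally, rescue for lack of efficacy |
|---|---|---|---|
| Rectal 5-ASA | failure | not listed: observed CDAI | not listed: observed CDAI |
| Oral 5-ASA (2a), 6-MP/AZA/MTX (3a-d), antibiotics (5a) | failure | failure | observed CDAI |
| Budesonide increase (1g), IV or rectal steroid start (1h, 1i) | failure | failure | observed CDAI |
| Oral steroid or budesonide start, oral steroid increase (1a-1f) | failure | failure (increases at the SAP's dose threshold) | failure if longer than 7 days (same threshold) |

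The first row is a mismatch on either reading. The second and third rows are mismatches only on the literal reading.

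**2. Look for text that closes the gap.**
- Intercurrent event 2 is undefined in SAP 5.3.2.1. In the protocol, 'prohibited' heads a different list (6.5.3: other immunomodulators, biologics, experimental drugs), and the SAP Table 2 footnote uses a similar list for endoscopic response.
- SAP Appendix 2, on changes from the protocol's planned analyses, mentions only COVID-19 handling.
- SAP 5.3.3 has no analysis with a wider medication trigger. Estimand 2 changes only events 4 and 5, Estimand 3 uses the same event list, and the exploratory observed-CDAI analysis removes failure scoring altogether.

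**3. Reproduce the plan's own precision.** Inputs from SAP section 3 and 1.2: difference 60, SD 93, 54 active and 36 placebo, two-sided alpha 0.1.
- SE = 93 x sqrt(1/54 + 1/36) = 20.0.
- Power = Phi(60/20.0 - 1.645) = Phi(1.35) = 0.912, in line with the stated 90%.
- P(80% lower bound at least 40 | true difference 60) = 1 - Phi((40 + 0.842 x 20.0 - 60)/20.0) = 0.563.

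**4. Effect of one participant.** The difference is placebo change minus active change. Scoring an on-rescue change of -100 as 0:
- in a placebo participant, raises the difference by 100/36 = 2.8 points;
- in an active participant, lowers it by 100/54 = 1.9 points.

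**5. Illustration for the literal reading.** The documents give no rescue rate, so the rescue inputs here are assumptions. Trials were simulated from the SAP Attachment 2 means, covariances and SES-CD mixture (20,000 trials, 54/36, half Bio-IR). Week 12 CDAI change was analysed by ANCOVA on treatment, population and baseline. The rescued are a share of those whose Week 4 change lies between -50 and 0 (about 10 of 54 active, 8 of 36 placebo). With no rescue the difference is 60.0, the SE 20.2, and the CDAI criterion is met in 55.9% of trials. The SES-CD part uses the SAP's mean wording and there is no interim look, so this is not a reproduction of the protocol's 87%.

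Shift = difference scored as observed minus difference scored as no change, in CDAI points:

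| Share rescued, active / placebo | Rescue effect 0 | 50 | 100 |
|---|---|---|---|
| 10% / 10% | +0.65 | +0.47 | +0.29 |
| 20% / 20% | +1.27 | +0.90 | +0.53 |
| 30% / 30% | +1.89 | +1.34 | +0.79 |
| 10% / 30% | -1.15 | -3.55 | -5.95 |
| 30% / 10% | +3.69 | +5.36 | +7.03 |

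For equal 20% shares and a 50-point effect:
- the shift in single trials has a 5th-95th percentile range of -9.2 to +10.6;
- the CDAI criterion is met in 55.1% (observed) v 53.6% (no change);
- CDAI or SES-CD success is met in 89.3% v 88.3%, with that call differing in 4.4% of trials.

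With no true difference and equal 20% shares, the shift is under 0.1 and the CDAI criterion is met in 0.3% either way.

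The small shift at equal shares arises because rescued active participants have, on average, larger Week 12 falls than rescued placebo participants. If both arms had the same on-rescue fall X, the shift would be (active share - placebo share) x X, which is zero at equal shares.

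**The case against.** A reader might infer that the SAP scores every rescue for lack of efficacy as observed. The documents do not establish that.
- Rules 1a-1f split reasons in two: immediate failure for worsening, and failure only after 7 days for other reasons. That tolerance suits non-Crohn's use such as asthma or surgery, which protocol 6.5.1 also sets apart. It suggests that 'worsening' may simply mean any Crohn's reason.
- The discontinuation rule names lack of efficacy separately, but beside an *adverse event* of worsening. It lists reasons for stopping drug and does not define the word for the medication rules.
- Protocol Appendix 8 separates lack of improvement from worsening, but it concerns eligibility after earlier ustekinumab.

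These points stand, so the literal reading is possible but not shown to be intended.

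Other points on that side:
- Protocol 6.5.2 says 'may be', and protocol section 9 leaves analysis detail to the SAP. This weakens the conflict, but 6.5.1 remains unconditional and SAP Appendix 2 declares no narrowing.
- Intercurrent event 2 has no worsening condition and might catch these cases. It might, but nothing says so.
- Protocol 4.2.1 says study drug should stop if additional therapy is needed, so the affected group may be very small. However, 6.5.1 and 6.5.2 expressly allow continued dosing after rescue.
- The Master protocol may hold the same or fuller rules. It is not among the documents and cannot be checked.

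None of this supplies a rule for rectal 5-ASA.

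**Conclusion.** The concern holds in limited form. The rectal 5-ASA omission is a mismatch with protocol 6.5.1 however 'worsening' is read, subject only to what the undefined intercurrent event 2 or the Master protocol may add. The undefined trigger in rules 1g-1i, 2a, 3a-d and 5a is an ambiguity in primary-endpoint scoring, not a demonstrated error.

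The effect is probably small: 1.9 to 2.8 points per participant for an on-rescue change of -100, and a mean shift of about +0.9 in the central illustration against an SE of about 20. Larger mean shifts, up to about 7 points, need markedly unequal rescue between arms, which is an assumption. A reader might infer a biased primary result. The documents do not support that: they give no rescue rate, the direction depends on which arm has more such rescue, and the shift under no true difference with equal shares is negligible.

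Severity is minor to moderate. The case for acting is that the rule decides a primary-endpoint value and is cheap to settle in advance.

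**What to change.** Before unblinding, and preferably before the interim analysis:
1. Add rectal 5-ASA to rule 2a.
2. In the medication rules, replace the worsening condition with *as a treatment for Crohn's disease (lack of efficacy or worsening)*, and reword 1b, 1d and 1f as use of more than 7 days for non-Crohn's reasons.
3. State that intercurrent event 2 of the primary estimand means this list. Keep the separate list for endoscopic response.

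If a narrower trigger is intended, define 'worsening', state that rescue for lack of efficacy is analysed as observed, and correct protocol 6.5.1 to agree.

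Aligning protocol 6.5.2 ('may be') with 6.5.1 ('would be') is optional and can wait for the next amendment. The sponsor should also check the wording against the Master protocol.

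The cost is SAP wording. No new data are needed, because protocol 6.5 already has the indication of each therapy recorded in the CRF, and what participants may receive does not change. The downside is that a few more participants are scored as no change: in the 20% illustration, about 2 active (20% of 10) and 1.6 placebo (20% of 8).

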### **5.3.2. Estimand**

#### **5.3.2.1. Primary Estimand (Estimand 1)**

The primary estimand uses a Composite Strategy that considers meeting the treatment failure (TF) criteria as an unfavorable outcome. This strategy aims to achieve an objective treatment effect.

The primary estimand, the main clinical quantity of interest to be estimated in the study, is defined by the following components:

**Treatment:** Oral tablets CCI [REDACTED] for a 12 week period

- Experimental: JNJ-67864238 (PTG-200), CCI [REDACTED]
- Control: Matching Placebo tablets CCI [REDACTED]

**Population:** Participants with moderately to severely active Crohn's disease, The target population consists of men or women 18 to 75 years of age with moderately to severely active Crohn's disease of at least 3 months' duration, defined as a CDAI score  $\geq 220$  but  $\leq 450$  at Week 0, with an SES-CD score  $\geq 3$  by central endoscopy read. Participants with a screening SES-CD score  $< 3$  can be randomized and received at least one study dose if they have an elevated CRP ( $> 0.3$  mg/dL or 3.0 mg/L) or elevated fecal calprotectin ( $> 250$   $\mu\text{g/g}$ ). Participants must have colitis, ileitis, or ileocolitis previously confirmed at any time in the past by radiography, histology, and/or endoscopy. Participants must be biologic intolerant or refractory (Bio-IR) or biologic nonfailures (Bio-NF) and must be on a stable dose of at least 1 protocol-permitted therapy for the treatment of Crohn's disease prior to baseline and not receiving any protocol-prohibited therapies. For more details and for a complete list of inclusion/exclusion criteria, please refer to the protocol.

**Variable (Endpoint):** Change from baseline in the CDAI score at Week 12. Participants who have intercurrent events in categories 1-3 (defined below) prior to the Week 12 visit will have their baseline CDAI score assigned, regardless of the observed data.

### Intercurrent Events and Corresponding Strategies:

The following are the intercurrent events considered for this trial:

1. A Crohn's disease-related surgery (with the exception of minor procedures such as drainage of a superficial abscess or seton placement, etc.);
2. A prohibited change in CD medication;
3. Discontinuation of study intervention due to lack of efficacy or an AE of worsening Crohn's disease;
4. Discontinuation of study intervention due to COVID-19 related reasons (like missing the assessment visit due to COVID-19 quarantine, but excluding COVID-19 infection)
5. Discontinuation of study intervention due to reasons other than lack of efficacy or an AE of worsening Crohn's disease (including AE/SAE due to COVID-19 infection).

Intercurrent events (ICEs) in categories 1-3 will be handled by the composite strategy, and ICE category 4 will be handled by the hypothetical strategy (as if subjects would have not experienced this intercurrent event), and ICE category 5 will be handled by the treatment policy strategy. The composite strategy assesses the treatment effects not only based on the variable measurements, but also based on intercurrent events. This estimand acknowledges that having an intercurrent event in categories 1-3 is an unfavorable outcome, ie. baseline value will be used after ICEs. For subjects experiencing ICE category 4, CDAI data at all visits after an ICE will be set to missing with

assumption of missing at random. For ICE category 5, treatment policy strategy, the observed values after ICEs will be used, if available.

**Population-level summary:** The difference of change in the CDAI score at Week 12 between the Experimental treatment group and the placebo treatment group.

### 5.3.3. Analysis Methods

#### 5.3.3.1. Main Estimator (Analysis) for the Primary Estimand

The primary analysis will be based on the full analysis set which will include all participants randomized and who receive at least 1 dose of the study intervention. Participants in the efficacy analyses will be summarized according to their assigned treatment arm regardless of whether or not they receive the assigned study intervention. The primary endpoint will be analyzed based on the primary estimand.

Data used in the primary analysis (i.e. the main estimator for the primary estimand) include all values for change from baseline in CDAI score collected up to and including Week 12 for all participants in the primary efficacy analysis set (ie, those who were randomly assigned to study intervention and received at least one dose of study intervention). Any CDAI score collected after experiencing intercurrent event categories 1-3 will be replaced by the baseline observation for CDAI. For subjects experiencing ICE category 4, CDAI data at all visits after an ICE will be set to missing with assumption of missing at random. For ICE category 5, treatment policy strategy, the observed values after ICEs will be used, if available.

The main estimator for the primary estimand is based on the Mixed Effects Model for Repeated Measures (MMRM), under the Missing at Random (MAR) assumption for the missing responses, the missing data will be accounted for through correlation of repeated measures in the model, to test the difference between the experimental group and the placebo group. The analysis will use change in CDAI scores at post-baseline time points through Week 12 as dependent variables. The explanatory variables of the MMRM model will include the fixed, categorical effects of treatment, time, and treatment-by-time interaction, as well as the continuous, fixed covariates of baseline and baseline-by-time interaction. If the intervention cohort includes both Bio-IR and Bio-NF participants, then the biologic therapy status will be included in the MMRM model as well. An unstructured variance-covariance structure will be used to model the within-participant errors. The treatment comparison at Week 12 in terms of the least square mean difference and confidence intervals for decision making will be estimated based on this model.

The estimates for the primary estimand of the treatment difference between each experimental group and the placebo group will be provided by the difference in the least squares means (LSmeans). The 90% confidence interval (CI) for the differences in LSmeans and p-values will be calculated based on the MMRM. An unstructured covariance matrix for repeated measures within a subject will be used.

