A target of 90 Bio-IR and Bio-NF participants will be randomized to receive JNJ 67864238 CCI [REDACTED] or placebo in a 3:2 ratio using permuted block randomization, stratified by baseline Crohn's Disease Activity Index (CDAI) score ( $\leq 300$ ,  $>300$ ) and biological refractory status (Bio-IR, Bio-NF). The treatment arms for this study will be as follows: JNJ-67864238 CCI [REDACTED] (N=54) and Placebo (N=36). Of note, the sample size has been chosen to assess a level of efficacy consistent with that observed with systemically available biological therapies for Crohn's disease.

An overview of this study design is presented in [Figure 1](#) below:

**Figure 1:** Schematic Overview of Study Design

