### 3. SAMPLE SIZE DETERMINATION

The sample size determination is based on the overall population, including both Bio-IR and Bio-NF participants. To examine the hypothesis that JNJ-active is superior to placebo as measured by CDAI, sample size is planned to achieve desirable operating characteristics of a predefined decision-making framework through simulation. A 90 Bio-IR or Bio-NF participants will provide about 90% power when the true treatment difference is 60 (placebo – JNJ-67864238) with standard deviation of 93 in the change in CDAI at Week 12 for both Bio-IR and Bio-NF populations.

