### 5.3. Primary Endpoint Analysis

**Level of Significance:** In general, all tests will be performed at a 2-sided significance level of 0.1, unless otherwise specified. All interval estimations will be reported using 2-sided 90% confidence intervals (CIs).

Multiplicity adjustment consideration will be based on an overall type I error rate of 0.1 (2-sided). The hypothesis testing will be conducted in a hierarchical manner with the test on the primary endpoint conducted first and the tests on major secondary endpoints conducted next. Within the major secondary endpoints, the sequential gatekeeping approach in conjunction with graphical multiplicity control procedures will be applied. As the interim analysis (IA) will not lead to an early completion due to success, multiplicity adjustment is not required. Nominal p-values will be calculated for all treatment comparisons.

The efficacy analysis of the primary will be based on the full analysis set. Regardless of the actual treatments the participants received, efficacy data will be analyzed according to the initial randomization assignment for the treatment phase.

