**Attachment 2: Data Simulation**

To evaluate the operating characteristics of the study design, the following assumptions are made based on 3 completed clinical studies (C0743T26/CNTO1275 Ph2b, CNTO1275CRD3001, and CNTO1275CRD3002) conducted by the sponsor:

- The compositions of Bio-IR and Bio-NF populations are 50% each
- For Bio-IR population, the CDAI scores of the JNJ-67864238 [CCI] treatment arm and placebo treatment arm at Weeks 0, 2, 4, 8, and 12 are assumed to be (323,285,259,247,238) and (323,305,300,299,298), respectively. Similarly, for Bio-NF population, the CDAI scores of the JNJ-67864238 [CCI] treatment arm and placebo treatment arm at Weeks 0, 2, 4, 8 and 12 are assumed to be (302,245,208,180,176) and (302,271,254,241,236), respectively.
- The covariance matrix is assumed to be

$$\begin{pmatrix} 3844 & 3069 & 3100 & 3193 & 3255 \\ 3069 & 8100 & 7200 & 6489 & 5670 \\ 3100 & 7200 & 10000 & 7210 & 5250 \\ 3193 & 6489 & 7210 & 10609 & 7030 \\ 3255 & 5670 & 5250 & 7030 & 11025 \end{pmatrix} \quad \text{and} \quad \begin{pmatrix} 3600 & 2970 & 2565 & 3646 & 2520 \\ 2970 & 8100 & 5558 & 5670 & 4725 \\ 2565 & 5558 & 9025 & 6484 & 4988 \\ 3646 & 5670 & 6484 & 11025 & 7166 \\ 2520 & 4725 & 4988 & 7166 & 11025 \end{pmatrix}$$

for the Bio-IR and Bio-NF populations, respectively.

- In CNTO1275CRD3001 and CNTO1275CRD3002, an optional endoscopy substudy was conducted in a subset of study participants. Based on the collected data, change in SES-CD is assumed to have a mixture distribution - excessive zeros (no change) and a normal distribution. Therefore, 2 steps were utilized to simulate the change in SES-CD data.
  - Step 1: no change in SES-CD is simulated for 19% of JNJ-67864238 [CCI] treated participants and 32% placebo treated participants.

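### SAP 5.3.3.1 resets only CDAI scores collected after a treatment failure, so read literally a failure with no later score falls under MAR; missing Week 12 scores in non-failures also have two conflicting rules

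*SAP*

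**What the plan says.** The SAP describes the handling of intercurrent event (ICE) categories 1-3 (Crohn's surgery, prohibited medication change, stopping for lack of efficacy or worsening disease) in four places.

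- **5.3.1, Treatment Failure Rules:** "baseline values (at Week 0) will be assigned from the point of treatment failure onward". The same section says these rules take precedence over other data handling rules.
- **5.3.2.1, Primary Estimand:** participants with such an event before Week 12 "will have their baseline CDAI score assigned, regardless of the observed data". The paragraph on strategies repeats that baseline is used after the event.
- **5.3.3.3, Estimand 2:** categories 4 and 5 are to be treated like categories 1-3, and this is spelled out as baseline at all visits after the event.
- **5.3.3.1, Main Estimator:** the data are CDAI changes collected through Week 12. For categories 1-3, "Any CDAI score collected after experiencing intercurrent event categories 1-3 will be replaced by the baseline observation for CDAI". Missing responses are left to the MMRM under MAR.

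Separately, 5.3.1 (Definition of Endpoint) says that anyone who does not return, or has no CDAI at Week 12, counts as unchanged from baseline. It does not limit this to treatment failures.

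**The concern.** The word *collected* in 5.3.3.1 leaves a gap. A participant who meets a failure criterion and has no CDAI afterwards has no score to replace. The only remaining instruction in that section is MAR, so the model would predict the Week 12 value from comparable participants who stayed. A failure who keeps attending gets zero change. Two participants with the same event would then be scored differently because one left, and the composite strategy would not be applied to the one who left.

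The contrast within 5.3.3.1 invites this reading: its next sentence, on category 4, does refer to all visits after the event. The section is also where a programmer would look for the derivation, and it supplies the confidence bounds used for decisions.

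For participants who are not failures the conflict is sharper. 5.3.1 assigns no change to a missing Week 12 score and 5.3.3.1 applies MAR. The override rule does not reach them. Category 4 shows the clash: 5.3.2.1 sets later scores to missing under MAR, and 5.3.1 would then turn the missing Week 12 score into no change.

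**Working it through.** **1. The plan's own figure.** SAP section 3 says 90 participants "will provide about 90% power when the true treatment difference is 60", "with standard deviation of 93 in the change in CDAI at Week 12". Allocation is 3:2 (54 active, 36 placebo), and "all tests will be performed at a 2-sided significance level of 0.1".

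- SE = 93 × √(1/36 + 1/54) = 20.0
- Power ≈ Φ(60/20.0 − 1.645) = 0.912; noncentral t with 88 df gives 0.908.
- The Attachment 2 covariance matrices give a pooled ANCOVA residual SD of 93.6 and power of 0.909.

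The stated figure reproduces. It assumes a Week 12 value for all 90, so it does not depend on this point.

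**2. Size by arithmetic.** Mean Week 12 improvements from Attachment 2:

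- Bio-IR: 323 − 238 = 85 active; 323 − 298 = 25 placebo
- Bio-NF: 302 − 176 = 126 active; 302 − 236 = 66 placebo
- 50:50 mix: 105.5 active, 45.5 placebo, difference 60

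Let pA and pP be the shares of each arm that are treatment failures with no Week 12 score. The documents give no such rate, so these are assumptions. If leaving is unrelated to outcome, MAR targets 60 and baseline assignment targets (1 − pA) × 105.5 − (1 − pP) × 45.5:

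| pA / pP | Baseline assigned | Left MAR |
|---|---|---|
| 5% / 5% | 57.0 | 60 |
| 10% / 10% | 54.0 | 60 |
| 15% / 15% | 51.0 | 60 |
| 5% / 10% | 59.3 | 60 |
| 10% / 20% | 58.55 | 60 |
| 5% / 15% | 61.55 | 60 |

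The gap is 105.5 pA − 45.5 pP. It changes sign when pP exceeds 105.5/45.5 = 2.3 times pA. The same formula applies to the second conflict if pA and pP are read as the shares of non-failures missing Week 12, again with missingness unrelated to outcome.

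**3. Size by simulation.** 3000 trials per scenario used the Attachment 2 means and covariances. Leavers miss only Week 12. The MAR fit is monotone maximum likelihood, which approximates the unstructured MMRM. The last column is the chance that the 80% lower bound for CDAI is at least 40. Each pair is baseline assigned, then MAR.

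| Leavers (active / placebo) | Difference | Power | Bound ≥ 40 |
|---|---|---|---|
| None | 59.3, 59.3 | 0.89, 0.89 | 0.54, 0.53 |
| Random 5% / 5% | 56.5, 59.4 | 0.87, 0.88 | 0.49, 0.54 |
| Random 10% / 10% | 53.5, 59.5 | 0.85, 0.88 | 0.42, 0.52 |
| Random 10% / 20% | 58.4, 59.8 | 0.90, 0.86 | 0.53, 0.53 |
| Random 5% / 15% | 60.8, 59.2 | 0.92, 0.87 | 0.57, 0.52 |
| No improvement at Week 8, about 3% / 8% | 58.5, 60.3 | 0.91, 0.90 | 0.53, 0.55 |
| No improvement at Week 8, about 7% / 16% | 55.6, 59.1 | 0.88, 0.86 | 0.49, 0.51 |
| No improvement at Week 8, about 14% / 32% | 52.4, 59.6 | 0.88, 0.81 | 0.43, 0.50 |

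Simulation error is about 0.4 points on a difference and 0.01 on a probability.

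**4. A milder case.** If the leaver fails earlier but still attends Week 8, that score is collected and set to zero change, which pulls the MAR prediction towards failure. With equal random loss of 5%, 10% and 15%, the gap falls to about 1.6, 3.3 and 4.9 points.

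**The case against.** The strongest reply is that the SAP already settles the treatment failure case. 5.3.3.1 never says that a failure without a later score is left MAR; it is silent. It ties the analysis to the primary estimand, 5.3.1 ranks the failure rules above other data handling, and Estimand 2 describes the category 1-3 handling as covering all visits. All of that stands, and it shows that baseline is the intent. A reader might infer that the SAP instructs MAR for failures who leave; the documents do not support that.

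Second, the affected group may be small. The Schedule of Activities (footnote c) says that stopping treatment is not automatic withdrawal and asks participants to return for all visits. This also stands, but it does not empty the group. Protocol 2.3.1 describes withdrawal from the study for participants who need protocol-prohibited medication, and an early termination CDAI before Day 71 falls outside the SAP's Week 12 window (Days 71 to 98).

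Third, a reader might infer that the literal wording overstates the drug effect. That is not established. With random loss of 5% active and 15% placebo, baseline assignment gives the larger difference (60.8 against 59.2), and power is higher under baseline assignment in several scenarios.

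Fourth, the CDAI bound is one half of an either/or success rule with SES-CD, in a framework that SAP Attachment 1 calls non-binding. This limits the consequence.

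None of this answers the conflict over missing Week 12 scores in participants who are not failures.

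**Conclusion.** The point holds as a wording gap and an adjoining conflict, both in the primary analysis.

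- **Treatment failures with no later CDAI:** applied literally, 5.3.3.1 gives a different Week 12 value from the one the primary estimand defines. The intent can be recovered from 5.3.1, 5.3.2.1 and Estimand 2, but the main estimator should not depend on that inference.
- **Other participants with no Week 12 CDAI:** 5.3.1 and 5.3.3.1 disagree, and no precedence rule resolves it.

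For treatment failures, the two handlings differ by about 1 to 7 CDAI points in the simulated scenarios, and by up to 9 by arithmetic at 15% equal loss. At 10% random loss in each arm, the chance of meeting the CDAI success bound is 0.42 with baseline assigned and 0.52 under MAR. These sizes rest on assumed leaver rates and on the Attachment 2 means and covariances, and the direction depends on the balance of leavers between arms. The planned power of about 90% is not affected.

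**What to change.** 1. **5.3.3.1:** state that from the first ICE in categories 1-3 onward, the CDAI at every scheduled visit through Week 12 is set to baseline (change = 0), whether or not a score was collected, and that MAR applies only to the remaining missing values.
2. **5.3.1, Definition of Endpoint:** in the same edit, delete the sentence giving no change to any missing Week 12 CDAI for the primary MMRM, or reconcile it with the MAR sentence. Without this, step 1 leaves the second conflict in place.
3. **5.3.3.3, Estimand 2:** keep the all-visit wording, which covers categories 1-5. Do not copy in the category 1-3 sentence, which would contradict it. In its analysis paragraph, clarify only that MAR covers values not preceded by any of those five categories.

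The cost is a few sentences and the matching derivation, with no new data. It should be settled before unblinding. The estimate may move in either direction.
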